**Table 1: Recommended Treatment and Follow-up Based on Diagnosis and Test Results**

Visual Field	Optic Nerve	IOP	Gonioscopy	Diagnosis	Recommended Treatment	Initial Follow-up	Second Follow-up
Abn	Abn	NL or high	Open-angle	Open-angle glaucoma	Eye drops or selective laser trabeculoplasty	4-6 weeks	4-6 months
NL	NL	NL or high	Occludable	Anatomically narrow-angle	Laser peripheral iridotomy	4-6 weeks	4-6 months
NL	Abn	NL	Open-angle	Glaucoma suspect	Observe	4-6 months	Refer to ophtho.

NL=normal, Abn=abnormal. *Source: American Academy of Ophthalmology, American Glaucoma Society*

**C.2.b. Preliminary Glaucoma CDC Results:** We have successfully partnered with Westat, an independent evaluation firm appointment by the CDC, to collect and analyze data for this project. Patients represent a diverse population with respect to gender, race, and ethnicity. Of the 1,290 people who had a community eye exam between 1/1/13 and 2/1/14, 66% are female. Mean age is 69, with 15% aged 50 to 59 years and 85% age 60+ (Table 2).

**Table 2: Demographics of Patients Examined**

Total Exams (n=1290)	African American	Caucasian	Asian	Hispanic
Number of people examined	825	194	194	77
Percentile	64%	15%	15%	6%

Of these people, 483 (37.4%) have been identified with previously undiagnosed glaucoma, glaucoma suspect, or anatomically narrow-angles. All required ongoing follow-up eye exams, a number that is higher than nationally reported statistics (Table 3). A total of 144 patients (11%) were diagnosed with age-related macular degeneration (AMD), DR, and visually significant cataracts that required follow-up evaluation.

**Table 3: Diagnoses of Patients Examined**

Total exams n=1290	Glaucoma	Glaucoma-Suspect	Narrow-Angle	Existing Glaucoma	Visually Significant Cataract	Macular Degeneration Diabetic Retinopathy	No Glaucoma
# Diagnosed	52	276	155	85	92	52	684
Percentile	4%	21.4%	12%	6.6%	7%	4%	52%

Thus far, cancellations and no-show rates have been minimal (20%) for initial and follow-up exams. This project has successfully detected glaucoma in this population and illustrates the need for a new healthcare delivery model for ongoing follow-up care. Considering the lack of success with glaucoma patient follow-up adherence in office settings, the proposed telemedicine detection program, combined with an enhanced intervention, may contribute valuable new scientific information.

Initial patient-satisfaction data obtained from post-exam surveys are described in Table 4. Generally, patients reported either “very satisfied” or “satisfied” in the overall eye exam experience, duration of exam, and quality of staff. In the preliminary study, 91% of patients said that they would be very likely to obtain a follow-up eye exam, which indicates potential for a sizeable benefit of the intervention relative to current practice. These data have been presented at the 2013 American Public Health Association Conference, 2013 CDC Vision Health Initiative Symposium and 2014 American Glaucoma Society Conference. They will be presented at the Association for Research in Vision and Ophthalmology annual meeting in Orlando, Florida in May 2014.

**Table 4: Satisfaction Survey Results**

Question	Very Satisfied	Satisfied	Dissatisfied	Very Dissatisfied
Satisfaction with the exam	82%	16%	0%	0.4%
Satisfaction with the duration of exam	57%	36%	5%	0.6%
Satisfaction with the staff	86%	12%	0.4%	0.6%
Convenience of location of exam	84%	13%	0%	1%

**C.2.c. Preliminary Cost Analysis Results:** Under the leadership of [name], MPH, we evaluated costs in order to identify potential efficiencies for refinements and translation of the project by other institutions or to other settings. The preliminary costs of this study are reported at \$143,830 (\$131 per examined patient). It took between 5 and 14 minutes for staff members to complete each step. The visual field test and the physician exam required the most time; human costs were reported at \$42.44/participant. Medical equipment contributed the most to the non-human costs, which were reported at \$87.34/participant. The cost/glaucoma detected was

used to measure the effectiveness of this program, and costs were reported at \$1,189/case of glaucoma detected. Costs for glaucoma suspects were higher: \$578/case. Any other eye detected disease was reported at \$116/case.

C.3. Wills Eye CDC Diabetes Demonstration Project (PI: [name]): In 2010, the Wills Eye Hospital Department of Research, under the leadership of [name]; [name], RD; and [name], MPH received a \$1.45 million Cooperative Agreement from the CDC to conduct a demonstration project titled *Improving Access to Eye Care Among Persons with Diabetes in Philadelphia*. The 5-year project aims to develop a database of patients with diabetes who received care at Wills Eye within the previous 10 years.

C.3.a. Aim 1 Results: The research staff conducted a retrospective chart review of 1,968 patients over age 40 with diabetes seen in 2011-2012 in the Wills Eye Primary Eye Care Clinic. These patients first visited the clinic between 1/2007 and 12/2010. The review evaluated individual factors that impact utilization of vision care, including demographic information, insurance, smoking status, medications, glasses prescription, dates of DFE, and first reported hemoglobin A1C and blood glucose levels. The primary outcome was timely DFE follow-up adherence following the initial visit. Overall, 41.6% of patients adhered to follow-up recommendations.

In a multivariate analysis conducted in the fall of 2012, patients with severe DR were more adherent than patients with mild DR (Odds ratio [OR]: 3.65; 95% Confidence Interval (CI): 2.84-4.69). Other variables associated with increased adherence were advanced age (OR: 1.46; 95% CI: 1.18-1.80), insulin use (OR: 1.33; 95% CI: 1.08-1.65), having reported A1C (OR 1.58; 95% CI: 1.26-1.98) or blood glucose levels (OR: 1.78; 95% CI: 1.43-2.22). Current smoking status was associated with decreased adherence (OR: 0.55; 95% CI: 0.43-0.71). Our team recommended that, to reduce vision loss from DR, interventions should target younger patients, smokers, and those with mild and moderate DR, all of whom are at-risk for poor follow up eye care. This study provides additional evidence that targeting at-risk populations beginning at age 40 is critical.

C.3.b. Aim 2 Results: To evaluate the effectiveness of a multi-pronged intervention on DFE adherence, we also conducted a prospective, single-blind, randomized, controlled trial of 521 patients with diabetes who were due for follow-up DFEs. Patients were randomly assigned to usual care or the intervention group. Patients in usual care (n=259) received a form letter reminding them to make an appointment and an automated reminder phone call the day prior to their scheduled visit. Intervention patients (n=262) received an educational brochure about diabetic eye disease, with a personalized letter encouraging them to schedule an eye exam. Two weeks after mailing the letter and brochure, a patient navigator called intervention patients to help schedule their eye exam. Intervention patients also received a reminder letter 3 weeks before their appointment, plus an automated phone call the day prior to the scheduled visit.

Patients were mostly female (66%) and African-American (70%), with a mean age of 61. Patients in the intervention group were significantly more likely to schedule (63% vs. 40%;  $P < 0.0001$ ) and attend their appointment (48% vs. 30%;  $P < 0.0001$ ) than those in usual care. The intervention significantly improved diabetic DFE adherence. This study provides additional evidence that using navigators to call patients, schedule appointments, address barriers, and provide educational information improves follow-up adherence to eye care appointments.

C.3.c. Network Study Results: Through our CDC Innovative Network for Sight Research Group (INSIGHT), Wills Eye collaborates with investigators at the Wilmer Eye Institute at Johns Hopkins, Bascom Palmer at the University of Miami, and the University of Alabama at Birmingham. This collaborative, pilot project tested the use teleophthalmology in people with diabetes at community locations. The Wills Eye Telemedicine Department Reading Center evaluated and interpreted all fundus photographs. The study evaluated patients' adherence to recommended follow-up eye-care after receiving this free eye screening in 4 different community

settings. All subjects were notified of their eye exam results within 3 weeks of screening and completed a telephone questionnaire 3 months after that. Each site recruited between 500 and 600 patients with diabetes, most of whom were female and between 45 and 65 years old. Racial/ethnic distribution varied by site by community location: Philadelphia had 68.7% African American, Alabama had 84.4% African American, and Miami had 41% Hispanic and 33.8% African American.

Of the 1,949 patients photographed, 24% showed signs of DR and 50% showed signs of ocular pathology (cataract, ocular hypertension, or glaucoma). Approximately 6% of patients showed signs of glaucoma suspect. Approximately 11% of the images were unreadable. Over 97% of patients at all sites were satisfied with their screening experience, and over 70% would be willing to pay for a similar service in the future. Three months following the screening, approximately equal proportions of patients with abnormal and normal results reported seeing an eye-care provider (35% vs. 32%, respectively).

Of those who had not followed up, the percentage of patients with abnormal versus normal results who planned on attending an eye appointment was similar (71% vs. 70%, respectively). This study demonstrates that non-mydriatic retinal photography in community settings is a viable screening method for DR and other ocular diseases. However, methods to increase follow-up adherence after outpatient screenings must be explored. Therefore, our proposed intervention aims to improve follow-up adherence in high-risk, newly diagnosed patients with glaucoma, glaucoma suspect, and other eye diseases detected in a community setting. We are ideally prepared to implement this study because of our established research infrastructure, commitment from community partners, and collaborations.

**C.4. Pediatric Adherence Program Results:** Wills Eye Hospital's collaborative efforts with community and public school-based outreach programs in underserved areas of Philadelphia identified children who need to be examined by an ophthalmologist. Past experiences have indicated that less than 5% of parents or guardians returned with their children to Wills Eye Hospital for a subsequent eye exam. In a unique 2013 initiative, Wills hired a pediatric medical social worker to track, assess, and reduce some of the psychosocial barriers that previously led to poor attendance rates. By implementing the Children's Eye Care Adherence Program (CECAP), the social worker's primary goal was to increase follow-up rates in underserved, often uninsured, children. A total of 1,200 children were included in the CECAP study. Children involved in the sample were screened at an annual free, day-long community event (Give Kids Sight Day) and through an Eagles Eye Clinic held at Wills Eye Hospital throughout 1 year. A total of 120 (10%) of children under age 19 failed the exam and required a subsequent ophthalmology follow-up visit. With continued support and intervention by a pediatric social worker, CECAP results for follow-up return rates with a pediatric ophthalmologist have dramatically increased – from less than 5% to 59.2% (n=120) (P<.001).

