Patients who smoked were less likely to obtain a DFE. It is important for glaucoma specialists to know the patient's blood pressure because diastolic readings below 60 mmHg are linked to increases in IOP measurements. In addition, a recent study suggests that high blood pressure and elevated body mass index (BMI) are positively associated with IOP in middle-aged and older Japanese people. Therefore, Visits 1 and 2 will take place in primary care settings, and we will document the patients' blood pressure, hemoglobin A1C, smoking status, BMI. Our approach will also include providing 360-degree communication between ophthalmologists and primary care physicians (PCPs) in order to improve detection, management, and follow-up.

**B.6. Expected Contributions to Public Health:** In addition to a reduction of vision impairment due to glaucoma, *Healthy People 2020* addresses impairments due to DR, age-related macular degeneration, cataract, and refractive error, noting that "visual impairment is associated with loss of personal independence, decreased quality-of-life, and difficulty maintaining employment". We suggest a new paradigm to detect patients at-risk for glaucoma and other eye diseases who also have limited access to eye-care by evaluating a telemedicine intervention at the health centers and PCP offices. Those with ocular disease will be referred within 1-month for a comprehensive dilated eye exam in the same location to confirm their diagnosis. We expect that this 5-year sustainable research project will further our understanding of glaucoma detection and management, with the potential for generalizability. Using short-term and long-term outcomes, as well as the cost analysis findings, we believe that this study will produce very meaningful results and contribute substantially to the field of public health. Also, the high-quality data of fundus photographs, their interpretation by glaucoma specialists, and confirmation examination, could be used to develop a software that would allow automated detection of glaucoma-suspicious discs. Such a tool could decrease the dependence on highly trained glaucoma specialists and have a far reaching effect on screening.

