**Table 9: Assessment of Adherence to Follow-Up Recommendations**

Recommended Follow-up	Number of visits per year considered adherent to recommendations
1-2 months	At least 6 visits per year with an eye care provider
3-6 months	At least 3 visits per year with an eye care provider
6 months	At least 2 visits per year with an eye care provider
12 months	At least 1 visit per year with an eye care provider

E.2.c. Primary Analysis for Aim 2: The primary outcome of the study is adherence to recommended follow-up in each year as described in section E.1.c. For each of the 3 years of follow-up, we have a dichotomous measure of adherence. We will model this longitudinal dichotomous outcome using Poisson regression within a generalized estimating equation (GEE) framework. Our model will include time (Year 1, 2, and 3), randomization assignment, randomization by treatment interaction, and baseline individual characteristics believed to be associated with adherence to follow-up, including age, diagnosis, vision impairment, and overall vision-related quality-of-life. Within this model, we will test 2 hypotheses.

First, we will compare randomization groups at Year 1 to test whether there are differences in early adherence. Second, we will calculate the average effect of randomization across Years 2 and 3 and test the long-term efficacy of the intervention. In both cases, we will estimate the overall relative risk of adherence along with its associated confidence interval. Each test will be performed with alpha=0.025. The primary analysis will include all patients who were randomized and have some adherence data (see section on missing data below).

E.2.d. Power for the Primary Analysis for Aim 2: Our estimated available sample size is given in Figure 2. We will randomize 300 patients (150 per group). Assuming up to 10% dropout where adherence cannot be calculated due to death or study withdrawal (i.e., final analysis dataset of n=135 per group), we calculate power to detect a 20% improvement in adherence under various assumptions of adherence under Usual Care. We have greater than 80% power to detect these differences using a two-sided chi-square test with alpha=0.025 (Table 10).

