**Table 10: Determination of Power Calculation**

Percent Adherence Under Usual Care	Percent Adherent Under Enhanced Intervention	Relative Risk	Power
35%	55%	1.57	86%
40%	60%	1.5	86%
45%	65%	1.44	86%
50%	70%	1.4	87%
55%	75%	1.36	89%
60%	80%	1.33	92%

E.2.e. Secondary Analyses for Aim 2: We will perform a secondary analysis to test for differences in the average number of appointments kept per person-year of follow-up. We will use Poisson regression to model

the total number of appointments after Visit 3 by randomization assignment. The offset term will be time under observation measured from Visit 3 to end of follow-up. We will adjust baseline for age, diagnosis, vision impairment, and vision-related quality-of-life. Change in continuous clinical and quality-of-life measures (IOP, visual acuity, NEI-VFQ, etc) will be modeled using mixed effects linear regression. Fixed effects will be time (treated continuously), randomization assignment, treatment by time interaction, age, and diagnosis. A first-order autoregressive correlation structure will be assumed to model correlation among repeated measurements. When possible, random slope and intercept terms may also be included. Effects of intervention on these measures will be tested by the significance of the interaction term.

E.2.f. Exploratory Analyses for Aim 2: We will consider whether the effect of the intervention differs by baseline patient characteristics of glaucoma severity (using VF mean deviation), and vision-related quality-of-life (NEI VFQ score). The primary model will be extended to include the interaction between these variables and randomization assignment to allow for estimation of intervention effects by baseline categories.

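### The adherence models do not name baseline smoking, which predicts adherence in the sponsor's own data and is recorded at Visit 1; adding it would be a small gain at almost no cost

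*Combined protocol and SAP*

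**What the plan says.** **Evidence on predictors.** C.3.a reports a multivariable analysis of timely dilated-exam follow-up in 1,968 patients with diabetes, of whom 41.6% adhered. It found that "Current smoking status was associated with decreased adherence (OR: 0.55; 95% CI: 0.43-0.71"), that "patients with severe DR were more adherent than patients with mild DR" (OR 3.65), and that advanced age was associated with better adherence (OR 1.46, 95% CI 1.18-1.80).

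**Collection.** For Visits 1 and 2, B.5 says "we will document the patients' blood pressure, hemoglobin A1C, smoking status, BMI". Table 5 ticks smoking status at both visits.

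**Randomisation.** Patients are normally randomised after Visit 2 (C.9). Those with IOP above 30 mm Hg skip Visit 2 and are randomised at Visit 1 (C.5.c). C.7.b uses random permuted blocks and describes no stratification.

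**Models.** For the primary outcome, "We will model this longitudinal dichotomous outcome using Poisson regression within a generalized estimating equation (GEE) framework" (E.2.c), adjusting for "baseline individual characteristics believed to be associated with adherence to follow-up, including age, diagnosis, vision impairment, and overall vision-related quality-of-life". For the appointment count, E.2.e states: "We will adjust baseline for age, diagnosis, vision impairment, and vision-related quality-of-life". Glaucoma severity, as visual field mean deviation, appears only in the exploratory interaction models of E.2.f.

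**The concern.** E.2.c sets its own test for a covariate: that it is thought to relate to adherence. On the sponsor's evidence smoking meets that test, and it lies further from the null than age, which was carried over. It is not named, and the documents do not say why.

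Two things are at stake. The first is precision: adjusting for a baseline predictor of the outcome narrows the interval for the relative risk and absorbs chance imbalance, which unstratified blocks do not control. The second is pre-specification. The E.2.c list is introduced by *including*, so it neither commits to smoking nor excludes it. An open list in the model that carries both primary tests leaves room to choose covariates after outcomes are known.

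**Working it through.** **1. The plan's power.** Inputs from E.2.d: 300 randomised, 10% loss, so 135 per arm; a "two-sided chi-square test with alpha=0.025"; a 20-point difference. (C.4.a gives 374 randomised; Table 10 rests on 300.)

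Power = Φ[(Δ√n − 2.241·√(2p̄q̄)) / √(p₁q₁ + p₂q₂)].

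At 35% vs 55%: (0.20·√135 − 2.241·√0.495) / √0.475 = (2.324 − 1.577)/0.689 = 1.084, so power is 86.1%. Across Table 10 this gives 86.1, 85.7, 86.1, 87.2, 89.1 and 91.6%, against the stated 86, 86, 86, 87, 89 and 92%. The table is reproduced.

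**2. Strength of the smoking association.** ln(0.55) = −0.598. SE = (ln 0.71 − ln 0.43)/(2 × 1.96) = 0.128. So z = −4.7. For age, z = 3.5. On the odds-ratio scale, 1/0.55 = 1.82 against 1.46. The documents do not give the coding of age, so this comparison is descriptive.

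**3. Variance explained.** Smoking prevalence *s* is assumed. Choose p₀ (non-smokers) and p₁ (smokers) with odds ratio 0.55 and (1−s)p₀ + s·p₁ = 0.416. Then R² = s(1−s)(p₀−p₁)² / (0.416 × 0.584).

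| Smokers | p₀ | p₁ | R² |
|---|---|---|---|
| 10% | 43.0% | 29.3% | 0.7% |
| 25% | 45.1% | 31.1% | 1.5% |
| 40% | 47.3% | 33.0% | 2.0% |

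**4. Effect on power.** Effective n = 135/(1 − R²). At 25% smokers this is 135/0.985 = 137.1, and power at 35% vs 55% moves from 86.1% to 86.6%. Over the whole range it reaches 86.3 to 86.8%.

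**5. Simulation.** A single-year modified Poisson model with robust variance, 135 per arm, 4,000 trials per scenario. The variance ratio is (empirical SE with smoking / SE without)².

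| Adherence | Smokers | Variance ratio | Power without → with smoking |
|---|---|---|---|
| 35% vs 55% | 20% | (0.1396/0.1403)² = 0.990 | 86.1 → 86.4% |
| 35% vs 55% | 25% | (0.1388/0.1398)² = 0.986 | 85.6 → 85.8% |
| 40% vs 60% | 25% | (0.1283/0.1291)² = 0.988 | 85.3 → 85.5% |
| 40% vs 60% | 35% | (0.1302/0.1315)² = 0.980 | 84.7 → 84.8% |
| 60% vs 80% | 20% | (0.0831/0.0832)² = 0.998 | 91.1 → 91.5% |

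A separate set of runs at 40% vs 60%, with 15 to 35% smokers, gave ratios of 0.988 to 0.997. The typical reduction is 1 to 1.5%, and every power gain is under one point.

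**6. Chance imbalance.** At 25% smokers, the SD of the between-arm difference in smoking is √(2 × 0.25 × 0.75/135) = 5.3 points, so a 95% range of ±10.3 points. Times the 14-point adherence gap in step 3, this shifts the comparison by at most about 1.4 points, against a 20-point target.

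**7. Severity, for comparison.** If the OR of 3.65 applied in full, smoking and severity together would give R² of 4.7% (20% smokers, 10% severe) or 7.6% (25%, 20%). Overall that is roughly 4 to 9% of variance in mid-range scenarios. Over wider assumed prevalences, analytic R² and simulation together span about 2 to 11%. Simulated power at 35% vs 55% rises from about 86% to 87.2-89.7%. With a severity OR of 1.5, the reduction is only about 2%.

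**The case against.** **The list is open, and the gain is slight.** E.2.c gives examples, not a closed set, so smoking could be added without departing from the plan. Stated power is already 86 to 92%, and omission causes no bias. All of this stands. It limits the point to a small improvement and incomplete pre-specification. It does not dispose of the point, because E.2.e has no such opening word and an open primary list is itself worth closing.

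**The smoking odds ratio may not carry over.** It comes from patients with diabetes in a hospital eye clinic, and from one follow-up exam instead of the 1 to 6 visits a year of Table 9. This stands too. But if smoking proved irrelevant, one extra term with about 270 patients would cost precision of order 1/270, about 0.4%.

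**A stronger reading is tempting:** that the plan discards two clear predictors, severity and smoking, both known before randomisation, and with them 5 to 9% of precision. The documents do not support it.
- The OR of 3.65 is for diabetic retinopathy grade. In the sponsor's glaucoma project, 431 of the 483 newly identified patients (276 suspects + 155 narrow-angle; 89%) were in categories that Table 1 defines by a normal visual field, so mean deviation should vary little among them.
- In the community screening study (C.3.c), 35% with abnormal and 32% with normal results saw a provider, an odds ratio of (0.35/0.65)/(0.32/0.68) = 1.14. That is not a severity contrast, but it cautions against carrying 3.65 over.
- E.2.b ties expected visits to severity. Sicker patients may face a harder target, so the association could shrink or reverse.
- Diagnosis, vision impairment and the NEI-VFQ are already in the model and carry part of severity. The step 7 gains are measured against no adjustment.
- Patients randomised at Visit 1 have no Visit 2 visual field.

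Nor is there a case for A1C on record. Adding it moves the variance ratio only from 0.914-0.945 to 0.911-0.941. It was a self-reported value in the eye chart there (B.5) but comes from the primary care record here.

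**Conclusion.** The point holds for smoking, as a minor improvement. The benefit is a variance reduction of about 1 to 1.5% and less than one point of power. This assumes that the OR of 0.55 carries over and that 10 to 40% of patients smoke. The calculation covers one year, not the three-year GEE, and does not include the four covariates already named. A reader might infer that the primary result is biased or underpowered without smoking. Neither follows: the comparison is randomised, and Table 10 reproduces without adjustment. Closing the covariate list is worth doing whatever the precision gain.

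**What to change.** In E.2.c, add current smoking at Visit 1 (yes/no) and replace the open-ended wording with a closed covariate list, fixed before outcome data are seen. Make the same addition in E.2.e. State that the Visit 1 value is used and that, for patients randomised at that visit, it is recorded before allocation. The C.5.c list of items documented at Visit 1 should mention smoking, to agree with B.5 and Table 5.

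Optionally, add baseline severity, but only if a class can be defined across diagnoses (for example, using the mean deviation of E.2.f for glaucoma) with a separate level for patients who have no Visit 2 exam. Otherwise, say in a sentence why it is left out. Do not add A1C.

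The cost is a wording change and one model term. No new data or patients are needed.
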